3.1.3 Study Stopping Criteria/Holding Criteria/Dose Escalation Process

There will be a review of the study data by the DMC when there is a reasonable possibility that the investigational vaccine caused any of the listed following adverse events based on the assessment of the Investigator in one or more participants at any dose. Vaccinations will be held pending this review:

- Death
- Life-threatening adverse event or life-threatening suspected reaction
- Serious suspected adverse reaction

- Suspected, unexpected, serious adverse reaction (SUSAR)
- Acute allergic reaction or anaphylactic shock following the administration of vaccine investigational product
- Anaphylaxis or bronchospasm, indicative of an immediate hypersensitivity reaction to study vaccine
- If any participant has any of the following:
 - ALT or AST >8 x upper limit of normal (ULN)
 - ALT or AST >5 x ULN for more than 2 weeks
 - ALT or AST >3 x ULN and (total bilirubin >2 x ULN or INR >1.5)
 - ALT or AST >3 x ULN with the appearance of fatigue, nausea, vomiting, right upper quadrant pain or tenderness, fever, rash, and/or eosinophilia (>5%)

The competent authority and Research Ethics Committee (REC) will be notified of a temporary halt within 15 days according to the local requirements. If, following the review of data, a recommendation is made by the DMC to resume study enrolment and vaccine administration, the DMC will record their judgment in a memorandum to the study file and notify the Sponsor. The DMC memorandum will be forwarded to the local Medical Monitor and Investigators.

3.1.4 *Duration of Study*

3.1.4.1 *Duration for Each Participant*

Cohorts 1-4: Up to 8 months (up to 1.5 months for screening and 6.5 months on the study with study vaccine given on Day 0).

Cohorts 5 and 6: Up to 4.5 months (up to 1.5 months for screening and 3 months on the study with study vaccine given on Day 0).

3.1.4.2 *Duration of Study*

It is planned that the study will take 16 months to implement, enrol and read out.

The end of the study is defined as the date of database lock.

3.2 *Discussion of Study Design*

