6.5 Participant Discontinuation

Participants have the right to withdraw from the study at any time for any reason, including their future care. The Investigator should however try to find out why a participant withdraws from the study and document the reason for withdrawal in the source documents and eCRF.

If there is a medical reason for withdrawal, the participant will remain under the supervision of the Investigator until satisfactory health has returned.

Participants who are withdrawn from the study prior to completion of the scheduled study procedures for any reason should complete the end of study visit assessments as far as possible.

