Unsolicited adverse events are other events meeting the criteria for adverse events (see [Section 8.2.1](#)) apart from those the participant is specifically asked about. Unsolicited

¹ In the event that they persist longer than 3 days then an adverse event will be recorded

non-serious adverse events will be collected from the date the informed consent is signed to 28 days post-vaccination. Hospitalisations, other SAEs and AESIs will be collected for the duration of the study.

Participants will collect unsolicited adverse events in the eDiary and these will be reviewed during clinic visits with the participant and relevant information (event term, start and end date, severity, causality, outcome and seriousness) collected and entered into the eCRF as described in [Section 8.2.3](#).

7.3.2 *Laboratory Safety Tests*

Laboratory safety tests will be performed at each of the timepoints according to [Table 2](#), as per [Sections 7.1.4.1](#) and [7.1.4.2](#). Extra laboratory safety tests may be performed if the Investigator deems them to be necessary to fully evaluate an adverse event. In the event that the Investigator elects to order non-protocol-specified laboratory tests, the Investigator must record the rationale for the tests and a determination of clinical significance of the result in the source documents. The Investigator must keep the local Medical Monitor informed of adverse events of clinical significance.

Abnormal results and findings will be discussed as applicable with the participant, and the participant will be referred for follow-up with their healthcare provider if necessary.

Results from the LFTs obtained on the study must be reviewed by the Investigator (or a designee who is a medically qualified study team member) and managed in accordance with the study centre procedures. The clinical significance of all results outside of the normal range will be determined by the Investigator and may be reported as an adverse event at the discretion of the Investigator.

7.3.3 *Physical Examination*

A skin, respiratory, cardiovascular, abdominal and lymphatic system examination will be performed at screening and pre-vaccination on Day 0. A symptom-directed physical examination will be performed at all other clinic visits if required. Results will be recorded as normal, abnormal and not clinically significant or abnormal and clinically significant.

7.3.4 *Vital Signs*

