10.1.2. Data Presentation

The specific format and content of each data presentation is shown in Section 14.

Summary tables will be presented by treatment group and also for safety summaries, demographic and baseline data, for all participants.

Within all Tables and Figures values for treatment group will be labelled as follows:

- “Healthy Participants – Low Dose”
- “Healthy Participants – High Dose”

- “Healthy Participants: Covid-19 vaccinated – ChAdOx1”
- “Healthy Participants: Covid-19 vaccinated – mRNA”
- “CHB Participants – Low Dose”
- “CHB Participants – High Dose”
- “Total”

For disposition summaries the participants that were screened but not vaccinated with ChAdOx1-HBV may be presented as:

- “Screen Failure”

Within Listings treatment groups will be identified as follows:

- “HP – LD”
- “HP – HD”
- “HP – HD – ChAdOx1”
- “HP – HD – mRNA”
- “CHB – LD”
- “CHB – HD”
- “SF”

And the ordering of treatment groups shown here represent the order they will appear in Tables.

The scheduled protocol visits will be labelled in the report presentations as follows:

- “Screening”
- “Day 0 – pre dose”
- “Day 0 – post dose”
- “Day 1”
- “Day 7”
- “Day 14”
- “Day 28”
- “Day 56”
- “Day 84”
- “Day 168”

Within summary presentations it is envisaged that only scheduled protocol visit values will be used for post-baseline time points. Within the clinical database, a number of data points may be labelled as unscheduled. These data points will be included within participant Listings only. However, at the DRM the occurrence of such non-scheduled data will be reviewed for each participant to decide if (and how) any such data point(s) should be included within summary presentations. Any such decisions will be documented in the DRM minutes.

Where duplicate information is collected (and reconciled) on both the CRF and on the non-CRF vendor data transfer(s) (e.g. sampling date) then only the CRF recorded information will be included in participant listings.

All variables will be listed to the same number of decimal places as reported. Descriptive statistics for all endpoints that are continuous will have the following summary statistics presented in the following order: n, mean (rounded to one more decimal place than recorded), standard deviation (rounded to two more decimal places than recorded), median (rounded to one more decimal place than recorded), minimum (as recorded), and maximum (as recorded).

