10.8.3. Laboratory Variables

The following haematology and chemistry (including Liver Function) parameters will be included within data presentations (and presented in the units as shown):

- Haematology: Haemoglobin (g/L), White Cell Count ($10^{**9}/L$), Platelets ($10^{**9}/L$), Haematocrit (L/L), Red Cell Count ($10^{**12}/L$), Mean Cell Volume (fl), Mean Cell Hgb (pg), Mean Cell Hgb Concentration (g/L), Neutrophils ($10^{**9}/L$), Lymphocytes ($10^{**9}/L$), Monocytes ($10^{**9}/L$), Eosinophils ($10^{**9}/L$), Basophils ($10^{**9}/L$), APTT (secs), Fibrinogen (g/L), PT (secs), INR.
- Chemistry (including Liver Function): Sodium (mmol/L), Potassium (mmol/L), Urea (umol/L), Creatinine (umol/L), Total Bilirubin (umol/L), ALT (IU/L), AST (IU/L), Gamma GT (IU/L), Alkaline Phosphatase (IU/L) and Albumin (g/L).

Any other laboratory parameters collected as part of the study (including urinalysis) will only be included in listings. Laboratory data collected in different units to that shown will be converted to the above specified units (if possible) and both will be shown in the listings.

Toxicity grades will be calculated for relevant laboratory parameters, as per Appendix 1 of the study protocol (Section 15.1**Error! Reference source not found.**). Shift tables will be presented showing

changes in each toxicity grade from the baseline grade to the maximum post-baseline grade for each treatment group.

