Programming Note: The parameters will not be available for all participants at all visits. For healthy participants we should only expect hepatitis B surface antigen, hepatitis B surface antibody and hepatitis B core antibody.

Listing 16.2.6.3
ELISpot

Cohort	Participant	Visit	Date	Lab Test	Sample	IFNG SFC/10 ⁶ PBMC Background Corrected
xxxxxx	xxxxxx	Day x	ddmmYYYY	Genotype C/ Control	xxx	xx

Cohort	Participant	Visit	Date	Lab Test	Stimulating Condition	Sample	Result
xxxxxx	xxxxxx	Day x	ddmmYYYY	Genotype C/ Genotype D	xxxxx	%CD4_CD154 %CD4_IFNG %CD4_IFNG+IL2 %CD4_IFNG+TNFa %CD4_IFNG+TNFa+ IL2 %CD4_IL2 %CD4_IL2+TNFa %CD4_TNFa %CD8_CD107a %CD8_IFNG %CD8_IFNG+IL2 %CD8_IFNG+TNFa %CD8_IFNG+TNFa+ IL2 %CD8_IL2 %CD8_IL2+TNFa %CD8_TNFa CD4_CD107a_MFI CD4_IFNG_MFI CD4_IL2_MFI CD4_TNFa_MFI CD8_CD107a_MFI CD8_IFNG_MFI CD8_IL2_MFI CD8_TNFa_MFI	xxx

Listing 16.2.6.5
Neutralising Antibody Sample Collection

Cohort	Participant	Visit	Date	Time
xxxxxx	xxxxxx	Day x	ddmmyyy	

Listing 16.2.7 Adverse Events						
Cohort/ Participant	Adverse Event (verbatim) Preferred Term / MedDRA SOC [1]	Start Date (study day) / Stop Date (study day)	Severity [2]	TE [3] / Serious	Special Interest / Related to Study Drug	Outcome Treatments Provided
xxxxxx / xxxxx	xxxxxxxxx / xxxxxxxx / xxxxxx	ddmmmyyy (xx) / ddmmmyyy (xx)	Grade 1/ Grade 2/ Grade 3/ Grade 4	Yes/No Yes/No	Yes/No Yes/No	xxxxxxxxxxxx

[1] MedDRA Version 22.1.

[2] Event Severity: Grade 1 = Mild, Grade 2 = Moderate, Grade 3 = Severe, Grade 4 = Life Threatening and Grade 5 = Death.

[3] TE = Treatment Emergent. An event is considered vaccine-emergent if the start date of the adverse event is on or after vaccination.

Programming note(s):

Only participants with AEs will be shown in this listing.

Listing 16.2.8.1
Haematology

Parameter	Cohort	Participant	Study Day	Date	Standard Result	Unit	Range		Clin. Sig.	Flag	Toxicity Criteria	Toxicity Grade
							Low	High				
xxxx	xxxxxx	xxxxxx	xxxx	ddmmyy/yy	xx.x	xx	xx.x	xx.x	xx.x	○	Yes/N	H/L

= Baseline grade.
* = Maximum post-baseline grade.

Programming Note(s) :

List by parameter first, then subject and then day/date.
If more than one Toxicity criteria apply to a laboratory parameter (e.g. hyper and hypo) then list them all.
Include all data collected, including any unscheduled data.
If there is a tie for the maximum post-baseline result then all should be flagged.

Repeat for the following listing:
16.2.8.2 Chemistry (including Liver Function Tests).

Listing 16.2.8.3
Urinalysis

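### Shift tables labelled maximum post-baseline grade use scheduled visits only by default, so they can miss a peak that the source listings flag

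*SAP*

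**What the plan says.** SAP 10.1.2 gives the general rule: "Within summary presentations it is envisaged that only scheduled protocol visit values will be used for post-baseline time points". Of values labelled unscheduled in the database it says: "These data points will be included within participant Listings only". It then provides an exception. The data review meeting looks at such data for each participant "to decide if (and how) any such data point(s) should be included within summary presentations", and its decisions are minuted. SAP 10.1.4, on missing data, again limits reporting to observed data at scheduled visits.

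SAP 10.8.3 defines the laboratory shift tables as showing "changes in each toxicity grade from the baseline grade to the maximum post-baseline grade for each treatment group". SAP 10.8.4 uses the same definition for vital signs. In the SAP 13.2 list, Tables 14.3.4 to 14.3.6 are the only tables built on the safety laboratory and vital-sign assessments.

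The shells for Listings 16.2.8.1 (repeated for 16.2.8.2) and 16.2.9 mark each participant's maximum post-baseline grade and instruct the programmer: "Include all data collected, including any unscheduled data".

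Protocol section 6 requires additional visits or assessments, for example those made to assess adverse events, to be entered in the eCRF as unscheduled. Protocol 7.3.2 says: "Extra laboratory safety tests may be performed if the Investigator deems them to be necessary to fully evaluate an adverse event". Under Protocol 6.5, participants who withdraw early "should complete the end of study visit assessments as far as possible".

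**The concern.** A maximum over follow-up is meant to catch the worst value, whenever it was measured. Under the default, the tables show the maximum over scheduled visits while their label promises more.

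The values left out are not a random subset. Unscheduled tests are often done because something prompted them, so any understatement falls on participants with a possible safety problem. Liver tests matter most here. Protocol 3.2 names liver toxicity as the risk to be minimised in CHB participants, and the holding criteria in Protocol 3.1.3 include ALT and AST thresholds. One of these, "ALT or AST >5 x ULN for more than 2 weeks", has a duration shorter than every scheduled gap after Day 28, so a test that settles it soon after two weeks would have to be unscheduled.

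**Working it through.** The plan states no figure on this point, so there is nothing to reproduce. The check is mainly a comparison of texts.

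**1. Does anything lift the scheduled-only default for the shift tables?** SAP 10.8.3 and 10.8.4 do not mention it. The Table 14.3.4 shell, reused for 14.3.5 and 14.3.6, counts participants with at least one post-baseline result but does not say that unscheduled results are included. The only route in is the data review meeting, which has no stated criterion.

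**2. Do tables and listings use the same data?** By default, no. The listings take the maximum over all results and the tables over scheduled results. For one participant the listing flag can therefore exceed the table grade.

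**3. Is baseline treated the same way?** No. SAP 10.1.1 takes the last non-missing value before vaccination, and the scheduled-only rule in 10.1.2 covers post-baseline values. An unscheduled result can set the baseline grade but, by default, not the post-baseline maximum.

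**4. Is the restriction declared as a change?** Protocol 10.2.2.6.2 planned the worst change per participant and counts of Grade 3 or 4 results, with no scheduled-only limit. SAP section 11 declares fewer types of presentation but does not mention this restriction.

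**5. How much room is there between scheduled tests?** From Protocol 3.1.2, laboratory days are 0, 7, 14, 28, 56, 84 and 168 in cohorts 1-4 (gaps 7, 7, 14, 28, 28, 84 days; total 168) and 0, 7, 14, 28 and 84 in cohorts 5-6 (gaps 7, 7, 14, 56; total 84). Assume that an elevation lasts D days and that its onset is uniform over follow-up; neither assumption is in the documents. The share of onset times for which it falls wholly between scheduled tests is sum of max(0, gap − D) divided by total days:

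| D (assumed) | Cohorts 1-4 | Cohorts 5-6 |
|---|---|---|
| 7 days | (7+21+21+77)/168 = 126/168 = 75% | (7+49)/84 = 56/84 = 67% |
| 14 days | (14+14+70)/168 = 98/168 = 58% | 42/84 = 50% |
| 28 days | 56/168 = 33% | 28/84 = 33% |

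These shares show only that a peak can fall between visits. They do not say how often one will occur or be tested.

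**6. A constructed example.** Suppose a CHB participant has ALT 9 x ULN at an unscheduled Day 40 test, 2 x ULN at Day 56, and nothing higher at any other scheduled visit. On the SAP 15.1 scale these are Grade 3 (5.1-10 x ULN) and Grade 1 (1.1-2.5 x ULN). Listing 16.2.8.2 flags Grade 3. If the meeting leaves the value out, Table 14.3.5 shows Grade 1. With no other such case, the share of the dose group of 6 at Grade 3 or above is 1/6 = 16.7% with the value and 0/6 = 0% without it. One participant would be 1/5 = 20% of a cohort of 5 and 1/15 = 6.7% of a cohort of 15. The table's own percentages use row totals, so they would match only if the whole group shared one baseline grade.

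**The case against.** The SAP may already allow the full maximum. The rule in 10.1.2 is framed around time points, which a maximum over follow-up is not, and the same section refers to the shells for the content of each presentation. The table shell states no scheduled-only limit, and the listing shells include unscheduled data. This reading is possible, but 10.1.4 points the other way, so two programmers could build different tables from the same text.

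The default is also soft. It is worded as an expectation, and the meeting can add values before database lock. The study is open-label and its safety summaries are purely descriptive, so there is no blind or test to protect. That answers any complaint about timing. What stands is that the decision has no criterion.

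No value is lost. All collected data are listed, the maximum is flagged, and SAP section 11 openly sends readers to the listings because numbers are small. Protocol 8.2.1.1 usually treats a Grade 3 or higher abnormality as an adverse event. This backstop is real but partial: under Protocol 8.2.2 non-serious events are recorded only to Day 28, and Protocol 7.3.2 leaves reporting of out-of-range liver tests to the Investigator's discretion.

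A reader might infer that early-withdrawal results are excluded as unscheduled. The documents do not support that. Protocol 6.5 calls them end of study visit assessments, so sites may enter them under that visit and they would then count as scheduled. The SAP's visit labels include no early-withdrawal visit and it gives no mapping rule, so the status is unclear.

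**Conclusion.** The point stands as a conflict within the SAP. Followed as written, the default gives tables that can understate the worst grade, under a label that says otherwise, and that can disagree with their own source listings. It rests on reading 10.1.2 and 10.1.4 as governing the shift tables and on the data review meeting not adding the value.

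The size is unknown, because the documents give no expected frequency of unscheduled tests. The interval shares and the change from 16.7% to 0% are illustrations under stated assumptions. A reader might infer that liver signals would go unseen in the trial. The documents do not support that: the values stay in the listings, and the holding criteria lead to review by the Data Monitoring Committee without reference to Table 14.3.5. The weakness is in the reported summaries, and it is worth correcting because they are the only tables of these assessments.

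**What to change.** Add to SAP 10.8.3 and 10.8.4, as a stated exception to 10.1.2 and 10.1.4: *The maximum post-baseline grade is taken over all post-vaccination results, including unscheduled results and any collected at early withdrawal.* Keep the scheduled-only rule for by-visit summaries. Repeat the sentence as a footnote to the Table 14.3.4 shell, which also serves 14.3.5 and 14.3.6, so that the tables agree with the flags in Listings 16.2.8.1, 16.2.8.2 and 16.2.9. Early-withdrawal results then count towards the maximum however they are labelled.

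The cost is a sentence and a short change to the table specification; no new data are needed. The small downside is that participants tested more often have more chances of a high grade, which a footnote can state.

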10.1.3. Statistical Testing and Estimation

No formal statistical analysis is planned.

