Blood samples will be tested for:

- In all participants:
 - HIV antibodies
 - HCV antibodies
- In Healthy Volunteers: qualitative HBsAg, HBsAb, HBcAb
- In CHB participants: quantitative HBsAg, HBeAg, HBcAg, anti-HBs, anti-HBe, anti-HBc, HBV DNA, pgRNA, HDV serology

7.1.4.4 *Urinalysis*

A urine sample will be collected in a sterile container for dipstick urinalysis. The following will be tested: blood, bilirubin, glucose, ketones, leucocytes, nitrite, pH, protein, specific gravity and urobilinogen. The Investigator may order additional urine tests to be performed.

7.1.5 *Urine Pregnancy Test*

A urine pregnancy test will be performed in female participants of childbearing potential at screening and confirmed to be negative pre-vaccination on Day 0, as per local standard procedures and at each of the timepoints according to [Table 2](#).

7.2 **Immunogenicity Assessments**

Immunogenicity samples (PBMCs) will be taken for planned and potential exploratory analyses at each of the timepoints according to [Table 2](#).

Immunogenicity studies will include (but are not limited to) analysis of samples ex vivo by multiparameter flow cytometry (including Mean Fluorescence Intensity measurements) and ex vivo IFN- γ ELISpot assays. The latter will be used for epitope mapping. Innate immune responses will be measured primarily by RNA sequencing of blood and may be assessed in other assays if cell numbers permit. Additional immunogenicity assessments may be performed.

7.2.1 *Secondary Outcomes in Blood Samples*

Peripheral blood mononuclear cells will be isolated from blood samples taken at each of the timepoints according to [Table 2](#), and tested for recognition of overlapping HBV peptide pools using ICS for multiple cytokines including, and not limited to IFN- γ , and will be analysed by multiparameter flow cytometry to obtain frequencies of HBV-specific T cells within CD4+ and CD8+ T cell subsets before and after vaccination (magnitude of vaccine-induced response). The mean/median fluorescence intensity of cytokine signals will be determined to provide a composite assessment of HBV-specific T cell avidity.

Serum blood samples in CHB participants will be used for analysis of HBV DNA, HBeAg, HBeAb, HBsAg and HBsAb.

Blood samples of healthy participants in cohorts 5 and 6 will be used for analysis of total T cell response to ChAdOx1-HBV antigens using a peptide-stimulated ELISpot assay.

7.2.2 *Exploratory Analysis*

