10 STATISTICAL CONSIDERATIONS AND ANALYSIS PLAN

10.1 Sample Size Determination

No formal sample size calculation for cohorts 1 to 4 was performed and sample size is based upon feasibility considerations. The chosen number of participants is considered sufficient to meet the objectives for the study.

The sample size for cohorts 5 and 6 is based on the ELISpot results of ChAdOx1-HBV administered to healthy adults at a dose of 2.5×10^{10} which resulted in a mean of 1,000 +/-500 spot forming units in three adults who had samples examined by same day analysis at Oxford University. Assuming the same response in 15 volunteers in each cohort, the sample size is powered to detect a 45% decrease in the T cell response in the participants receiving prior AZD1222 compared to the Pfizer/Moderna mRNA COVID-19 vaccine.

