5.2. Secondary Objectives

- Determine the immunogenicity of ChAdOx1 HBV in (A) healthy participants and in (B) participants with CHB, virally suppressed with oral antiviral medication.
- Determine the effect of ChAdOx1 HBV on the level of hepatitis B surface antigen (HBsAg) in participants with CHB infection, virally suppressed with oral antiviral medication.
- Cohorts 5 and 6 only: Assess whether the receipt of prior ChAdOx1-SARS-CoV-2 vaccine (AZD1222) results in decreased T cell responses to ChAdOx1-HBV, when administered 10-18 weeks prior to ChAdOx1-HBV.

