6. STUDY DESIGN

This is a Phase 1, first-in-human study of ChAdOx1-HBV. The study will be conducted in 40 healthy participants and 12 participants with CHB and virally suppressed with oral antiviral medication. This will be an open-label, non-randomised dose escalation study comparing the safety, tolerability and immunogenicity of 2 different doses of ChAdOx1-HBV vaccine. T cell responses in healthy participants who have received a prior two-dose series of AZD1222 will be compared with those who have received at least two doses of the Pfizer mRNA COVID-19 vaccine or the Moderna COVID-19 vaccine. The study design is shown in Figure 1.

Participants will be screened in the period Day -42 to Day -1. Informed consent will be obtained before any study specific procedures are performed. Eligible participants will then attend the clinic to receive study vaccine on Day 0. Participants will be enrolled sequentially.

The study will investigate the study vaccine as shown in Table 1. On Day 0, an electronic diary (eDiary), tape measure and thermometer will be provided to perform self-assessment of local and systemic reactogenicity. All participants will then have a follow-up telephone call on Day 1 and return to the clinic for study assessments on Days 7, 14, 28, 84. Participants in cohorts 1-4 only, will also have follow up visits on Day 56 and Day 168. End of study visit procedures will be performed at the final visit.

Five healthy participants will be administered the low dose first (cohort 1). Dose escalation will only be initiated in the next 5 healthy participants (cohort 2) following Safety Monitoring Committee (SMC) review.

Six CHB participants will be administered the low dose (cohort 3) before the dose escalation is initiated in the remaining 6 CHB participants (cohort 4).

Thirty healthy participants (15 who have received two doses of AZD1222 [cohort 5] and 15 who have received at least two doses of either the Pfizer or Moderna mRNA COVID-19 vaccine [cohort 6]) will be dosed in parallel with the high dose used in cohorts 2 and 4.

The first participant in each of cohorts 1-4 will be assessed for 1 hour in the clinic post-vaccination in case of immediate adverse events (timed after the end of study vaccine administration). All other participants will be assessed for 30 minutes.

Five reviews of the safety, tolerability and available immunogenicity data will be performed by a SMC:

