7.2. Secondary Endpoints

- A multi-parameter index made of CD4+ magnitude, CD4+ avidity, and CD8+ magnitude
- Mean reduction in HBsAg titre at Week 12 (Day 84) and Week 24 (Day 168) post-vaccination (last visit)
- Proportion of CHB participants with hepatitis B e-antigen (HBeAg) and HBsAg loss
- Proportion of CHB participants with HBeAg and HBsAg seroconversion
- Reduction of hepatitis B deoxyribonucleic acid (DNA) levels
- Total T cell response to the antigens encoded by ChAdOx1-HBV as measured in a peptide-stimulated ELISpot assay

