8. SAMPLE SIZE

The number of participants is based on feasibility considerations rather than formal sample size calculations. A total of 10 healthy participants and 12 participants with CHB infection is considered sufficient to confirm the safety, tolerability and immunogenicity of ChAdOx1-HBV and to answer the objectives of the study before progressing to larger studies.

The sample size for cohorts 5 and 6 is based on the ELISpot results of ChAdOx1-HBV administered to healthy adults at a dose of 2.5×10^{10} which resulted in a mean of 1,000 +/-500 spot forming units in three adults who had samples examined by same day analysis at Oxford University. Assuming the same response in 15 volunteers in each cohort, the sample size is powered to detect a 45% decrease in the T cell response in the participants receiving prior AZD1222 compared to the Pfizer/Moderna mRNA COVID-19 vaccine.

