10.1.7. Multiple Comparison/Multiplicity

No statistical analysis is planned and therefore there are no multiplicity issues in this study.

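### Cohort 5 versus cohort 6 is the only comparison with a power statement, yet the SAP prespecifies no between-cohort ELISpot estimate, confidence interval, across-antigen response or main visit

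*SAP*

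**What the plan says.** SAP Section 5.2 gives cohorts 5 and 6 their own secondary objective: "Assess whether the receipt of prior ChAdOx1-SARS-CoV-2 vaccine (AZD1222) results in decreased T cell responses to ChAdOx1-HBV". SAP Section 6 says that "T cell responses in healthy participants who have received a prior two-dose series of AZD1222 will be compared with those" who had an mRNA COVID-19 vaccine. The endpoint in SAP Section 7.2 is "Total T cell response to the antigens encoded by ChAdOx1-HBV as measured in a peptide-stimulated ELISpot assay", and Protocol Section 7.2.1 says that blood from these two cohorts "will be used for analysis of total T cell response to ChAdOx1-HBV antigens using a peptide-stimulated ELISpot assay".

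Protocol Section 10.1 and SAP Section 8 base the size of these cohorts on ELISpot results from three adults (mean 1,000 +/-500 spot forming units): "Assuming the same response in 15 volunteers in each cohort, the sample size is powered to detect a 45% decrease". Cohorts 1 to 4 had no formal calculation.

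On analysis, SAP Section 10.1.3 (Statistical Testing and Estimation) says "No formal statistical analysis is planned", and Section 10.1.7 says "No statistical analysis is planned and therefore there are no multiplicity issues in this study". Section 10.7.2 summarises ELISpot responses and changes from baseline by treatment group, at each immunology timepoint, for Core, Pol1-Pol4, Pre S1/S2/S and Sli separately. Table 14.2.4 prints n, mean, SD, median, minimum and maximum. Its Total column pools participants, not antigens. Listing 16.2.6.3 gives participant-level background-corrected values.

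**The concern.** The comparison has a sample size rationale and a stated objective but no defined result. No cohort 5 versus 6 difference or ratio is specified, and no interval. No response across antigens is defined for an endpoint named as a total, and no visit is singled out, although the HBsAg endpoint in the same section names Days 84 and 168.

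These cohorts are 30 of the 52 planned participants. If the plan is followed as written, the question they were sized for is reported without a stated effect or its precision. Anyone who later wants an answer must choose the response, visit and contrast after open-label data are available. Side-by-side means without an interval also make it easy to read no visible difference as no interference.

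**Working it through.** **Inputs.** Mean 1,000 SFU, +/-500, 15 per cohort and a 45% decrease come from SAP Section 8 and Protocol Section 10.1. Neither document gives alpha, sidedness, power or scale, or says that 500 is an SD. Assumption: it is an SD. Post-baseline immunogenicity samples in these cohorts fall on Days 14, 28 and 84 (Protocol Section 3.1.2 and Table 2).

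**The plan's own figure.** Difference = 0.45 × 1,000 = 450 SFU. With a common SD of 500, SE = 500 × √(2/15) = 182.6, and 450/182.6 = 2.46.

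| Assumed alpha | Power at 15 per cohort, noncentral t | Power, normal approximation | n per cohort for 80% power, normal approximation |
|---|---|---|---|
| 5% one-sided | 77.6% | 79.4% | 16 |
| 5% two-sided | 66.3% | 69.3% | 20 |

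The stated 15 per cohort is therefore close to an 80%, one-sided 5% design on the raw scale, which neither document states.

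**What the SAP yields as written.** Four antigen combinations × three post-baseline visits = 12 pairs of cohort summaries, or 24 counting changes from baseline. None is designated as the answer.

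**Precision of the missing estimate.**

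- Common SD 500: t (28 df) = 2.048, and the half-width is 2.048 × 182.6 = 374 SFU (37% of 1,000). An observed drop of 450 gives 450 ± 374, or 76 to 824 SFU: about 8% to 82%.
- SD falling with the mean (500 and 0.55 × 500 = 275): SE = √((500² + 275²)/15) = 147.3. Welch df are about 21.8, t is about 2.075, and the half-width is about 306 SFU. An observed drop of 450 gives 144 to 756 SFU: about 14% to 76%.
- Uncertainty in the SD: with three adults (2 df, normal data assumed), the 95% interval for an SD of 500 is 500 × √(2/7.378) to 500 × √(2/0.0506), about 260 to 3,142. Scaling the common-SD half-width gives 374 × 260/500 = 194 to 374 × 3,142/500 = 2,350 SFU.

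**Whether other planned work supplies the estimate.** The cohort 5 and 6 paragraph of SAP Section 10.7.2 names an index of CD4+ and CD8+ magnitude and a neutralising antibody titre, and places T cell responses in listings. The analyses left outside the SAP are additional ICS work (Section 10.7.2) and the exploratory endpoints (Section 10.7.3). None is an ELISpot contrast between cohorts 5 and 6.

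**The case against.** The strongest reply is that this is a small, open-label, non-randomised Phase 1 study with safety as its primary objective. Protocol Section 10.2.2.1 calls most of the analysis descriptive and says only that immunogenicity data may receive further analysis, to be detailed in the SAP. That stands: the SAP does not breach the protocol, and no hypothesis test is owed.

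A second reply is that nothing is lost. Per-antigen contrasts can be worked out from Table 14.2.4, and a sum, its SD and any contrast can be computed from Listing 16.2.6.3. That also stands. A reader might infer that the total cannot be recovered from the planned outputs; the listing shows that it can. What remains is that no particular calculation is fixed in advance.

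A third is that *total* may mean T cells not separated into CD4+ and CD8+ subsets, rather than a sum over antigens. The documents do not settle this. Either reading still needs one named response, because four combinations are reported.

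A reader might also see two competing zeroing rules. Section 10.7.2 sets results not exceeding 25 to zero, while the Table 14.2.4 footnote mentions only values below zero. The rule in the text is explicit, so the footnote is better read as incomplete.

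**Conclusion.** The point holds as a gap in prespecification that should be fixed. The plan says "the sample size is powered to detect a 45% decrease in the T cell response in the participants receiving prior AZD1222", but defines no estimate by which such a decrease would be reported.

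Under a common SD of 500 with all 15 per cohort evaluable, the interval would be about ±374 SFU; if the SD falls with the mean, about ±306 SFU. Both rest on reading +/-500 as an SD. Because that figure comes from three adults, the half-width could lie anywhere from about 194 to 2,350 SFU.

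A reader might infer that the cohorts are underpowered or the sample size is wrong. The documents do not support that: the stated size is roughly reproduced under a one-sided 5% assumption, and the two-sided shortfall matters only if a two-sided test was intended, which is not stated. A reader might also infer that a result has been, or will be, selected after the fact. Followed literally, the SAP selects nothing, and any departure must be described in the clinical study report (SAP Section 4). The weakness is that the choice is left open.

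**What to change.** 1. In SAP Section 10.7.2, name the one ELISpot response on which the cohorts are compared: the participant-level sum over the HBV antigen combinations if *total* means across antigens, otherwise the response intended. State whether Sli is included. Keep the threshold of 25 as written there, and make the Table 14.2.4 footnote match it.
2. Name one main post-vaccination visit from Days 14, 28 and 84, with the others supportive.
3. For this objective only, replace Section 10.1.3 with a cohort 5 versus cohort 6 difference in means and a Welch 95% confidence interval, labelled descriptive and non-randomised. This matches the raw scale of Table 14.2.4 and of the sample size figures. Add a Hodges-Lehmann shift or a geometric mean ratio as a sensitivity analysis, and adjust Section 10.1.7 to agree.
4. In SAP Section 8, state alpha, sidedness, power and scale for the 45% figure, and whether +/-500 is an SD.

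The cost is minor SAP wording and one small analysis, with no new data or participants. The downside is that the interval may show the comparison to be imprecise, and the power may look less favourable once sidedness and scale are fixed.
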